
Remarkably, branch-chained fatty acids (particularly L-leucine) administration has been recently associated with decreased skeletal muscle autophagy and reversal of protein-breakdown signaling. Myostatin is one of the main players driving autophagy and blocking protein synthesis through inhibition of the mammalian target of rapamycin, and it has been found to be elevated in patients with cirrhosis. It is thought that hyperammonemia increases myostatin, then facilitating to impaired proteostasis with the end result of muscle loss or sarcopenia.(26) Finally, insulin-like growth factor 1 (IGF-1) is a trophic factor directly affecting muscle growth and repair, and it is known to be induced with exercise and L-leucine supplementation (Church. J Am Coll Nutr 2016;in press).

Although physical fitness is a modifiable risk factor, there are no studies to date assessing whether an exercise program aiming to improve cardiorespiratory endurance and physical fitness while on the waiting list could potentially improve posttransplant outcomes. One of the concerns with an exercise program in patients with cirrhosis and ESLD is its safety. Two of the perils that could possibly occur as a consequence of exercise are episodes of gastrointestinal (variceal) bleeding and/or HE. Although there are pathophysiologic and anecdotic evidence supporting that an increased risk for these complications is plausible, there are no clinical data to substantiate the concept. At least 9 published studies(4, 5, 11, 25, 27-30) have subjected patients with cirrhosis (\pm ESLD) to physical activity programs or exercise stress testing - intensity varying from a daily low intensity (estimated $VO_{2\max}$ of 35-50%) to a single bout of moderate-to-high intensity exercise ($VO_{2\max}$ 60-100%) - with no documentation of adverse reactions. Particularly no episodes of variceal bleeding or HE were observed. However, it is unknown whether such complications were intentionally investigated in any of the above-mentioned studies, as none of them was designed to identify and correlate such complications of ESLD to physical activity.

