In an interesting study, Garcia-Pagan *et al* submitted patients with cirrhosis to a low-to-moderate exercise regimen while measuring the hepatic venous pressure gradient (HVPG) and were able to find out that exercise increases the HVPG by 21% at a 50% maximum work load. This was followed by a return to normal after 5 minutes of stopping physical activity.(31) In a subsequent study from the same group, Bandi *et al* showed that the increase in HVPG during exercise could be abolished if the patient was given a beta-blocker before the exercise bout.(32) Since the HVPG is the best available marker to determine portal hypertension and the risk for variceal bleeding, data above suggest that the risk of variceal bleeding acutely increases during exercise, whenever the patient is not receiving a beta-blocker. However, our randomized clinical trial was able to show a decrease in the HVPG by the end of the study period in the active group contrasting the expected increase observed in controls (HVPG: -2.5 [-5.25 to 2] vs 4 [0.25 to 8], respectively, $p=0.007$).(33) This surprising finding brings to light that there might be some other benefits from physical fitness that we are yet unable to see. Moreover, no cases of variceal bleeding were observed in this and other clinical trials evaluating the effect of an exercise program in cirrhosis.(5, 25, 33)

Ammonia, a byproduct of nitrogen metabolism, is the most important factor associated with HE.(34) During exercise, and mostly under anaerobic conditions, breaking of ATP will result in net production of ammonia, what could expose patients with ESLD to hyperammonemia and episodes of HE. In sports medicine, the ammonia threshold, which corresponds to the deflection point at which ammonia production increases disproportionately during CRET (Figure 1c), has been used as a marker of exercise endurance. Actually, the increase in blood ammonia during exercise is directly related to the $VO_{2\max}$ such that a more efficient aerobic capacity is associated with higher ammonia thresholds (less ammonia production for same $VO_{2\max}$). Although the ammonia threshold grossly coincides with the inflection point defining the change from aerobic to

Title: A physical activity program in end-stage liver disease

PI: [name]

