All patients referred for an evaluation for liver transplantation, as well as patients with ESLD from hepatology clinics at UAMS, will be screened for study and invited to participate, when applicable. A total of 50 patients will be included in study. Inclusion and exclusion criteria will be as follows:

Inclusion criteria

1. Age 40 to 70.
2. Cirrhosis, any cause, defined as:
 - a. Biopsy-proven.
 - b. Two or more of the following: albumin <3.5 g/dL, INR >1.3, radiologic or endoscopic evidence of portal hypertension.
3. Creatinine <2.0 mg/dL.
4. Physiologic MELD \geq 10.
5. Decompensated cirrhosis with active or history of variceal bleeding, ascites, hepatic encephalopathy, or jaundice.
6. Potential transplant candidate as per UAMS criteria.

Exclusion criteria

1. Large gastric or esophageal varices with contraindication to use beta-blockers.
2. Persistent hepatic encephalopathy grades 2-4.
3. Prior diagnosis of hepatocellular carcinoma, or hepatic hydrothorax (with prior repeated thoracocentesis).
4. Cirrhotic cardiomyopathy or congestive heart failure, pulmonary vascular complications, known active coronary artery disease, syncope, and cardiac dysrhythmias.
5. Physical impediment to perform a cardiorespiratory fitness test.
6. Use of implantable defibrillator or a pacemaker.

Note: all inclusion / exclusion criteria will be obtained from routine investigations available during transplant evaluation, as part of the standard of care.

Description of Study Interventions

Physical Activity

After signing of informed consent patients will be given a Fitbit to measure all physical activity throughout the day. The Fitbit is a digital pedometer inside of a bracelet capable of continuously measuring all physical activities (24/7) and heart rate. Each subject should wear her/his bracelet during the whole duration of the study, for a total of 14 weeks. There will be a 1-week delay between enrollment into the study and the initial study's appointment, in order to obtain the baseline physical activity from each subject (corresponds to week -2, see Study Calendar). Physical activity and heart rate logs will be electronically downloaded to the investigator's computer during each follow up visit.

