The study will occur over a total of 14 weeks, although duration of the intervention will consist of 12 weeks. The first two weeks will serve the purpose of identifying the baseline physical activity of each participant. During the second week all baseline studies/determinations will be completed, with randomization occurring by the end of week 2. Allocation will be stratified by presence or absence of refractory ascites.

Follow up visits for behavioral therapy will occur every 2 weeks for the first 8 weeks, and then on a 4-weekly basis (only active group). Nutritional consultation will occur every 2 to 4 weeks throughout the study (both active and control group). During each visit, the EAA supplement jar will be inspected for percent emptiness (in analogy to a pill count) in order to quantify adherence. Bi-weekly phone calls will be made to all subjects to enhance adherence to recommendations. Standard of care investigations (blood chemistries, hematology and coagulation, liver function tests, etc.) will be ordered according to the needs of the patient and the criteria of the investigator or responsible clinician. Clinical status and complications from portal hypertension, particularly variceal bleeding and HE, will be systematically investigated on each visit.

Research Tests - Variables to Measure

Prior to randomization each subject will be scheduled to undergo all baseline investigations, as follows (see Research Calendar below):

Cardiorespiratory stress test (CRET) and anaerobic threshold (Week -1, Day 1)

CRET will be performed early in the morning on a fasting state, following the maximal incremental cycle ergometry protocol from our Pulmonary Physiology Laboratory, and in agreement with the American Thoracic Society.(38) Briefly, test consists on having the patient on a cycle ergometer performing a progressively increasing work rate until reaching: volitional exhaustion, or termination by the medical monitor. The Borg Rating of Perceived Exertion Scale will be used to help titrate intensity of work rate (aiming for a level of 13 to 17). Gas exchange measurement for

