A database will be created to accumulate all of the clinical information generated during this study. No identifiers, apart from name and DOB, will be collected. All data will be stored in databases kept in a study folder created at PI's computer (password-protected). Main database will include aforementioned identifiers, however, each subject will have a unique study ID assigned, and once an analytic table is created, all PHI will be removed from the table (after approval by the PI). Only this de-identified dataset with unique study ID's will be used for statistical analyses. Therefore, the risk to the privacy of the individuals will be minimized.

The access to the research folder and its contents will be restricted to the research staffs listed in this submission form. The PHI will be kept in the main database until completion of the study. The main database containing PHI will be kept in the study folder and will be never transferred out without de-identification of the data. No hard copy research data will be generated in this project.

In order to quantify the muscle mass at the level of L3, electronic copies of abdomen CT-scans with no identifiers will be shared with [name] from the University of Alberta, in Canada. After proper quantification an analytic table including unique study ID's will be sent back to UAMS for integration into the main database.

Risks and Benefits

CRET is a safe procedure and the risk for having a complication, such as an acute coronary syndrome is mostly related to underlying chronic disease. The risk of death varies as well, from 1 death in 20,000 - 70,000 tests, depending mostly on the presence of underlying heart disease. In cohorts including healthy subjects, no deaths or major complications have been observed. Since LT candidates have to undergo a thorough cardiopulmonary evaluation and patients with any moderate to severe cardiopulmonary condition are not considered transplant candidates the risks for any major complication or death in this study should equal zero. Moreover, the personnel taking care of CRET constantly monitors physiologic responses to exercise (including electrocardiogram monitoring), and are trained to stop the test whenever there are signs for an impending complications, and can immediately and effectively perform cardiac resuscitation.

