No complication is properly expected from the exercise program since each patient will tailor her/his own intensity of exercise according to individual fitness and symptoms that might occur while exercising (i.e. fatigue, or shortness of breath). Although there is a theoretical increased risk for variceal bleeding and HE, these complications have not been observed in prior studies. Moreover, the CRET and ammonia and lactic acid determinations (obtained with ammonia/lactate thresholds) would provide the investigator with some sense of risk for complications during intense exercise and could adequately advise patients at a higher risk for complications to avoid moderate to intense exercise.

The database containing PHI will remain within UAMS firewall and only used for specific research purposes in this project. Aggregated data will be analyzed and published, but specific data elements will not be made available. Further, subjects will not forfeit any rights by participating - their health care and eligibility for health benefits will not be affected in any way. Although a breach in confidentiality is always a risk when collecting personal information from patients, we believe this is small given the system that has been developed to obtain and handle data.

[figure not shown]
All participants might benefit from study by increasing their physical fitness and dietary habits during and after the study, and they will be able to keep their Fitbit to continue monitoring physical activity.

Ethics

[figure not shown]
This study will be conducted according to US and international standards of Good Clinical Practice (FDA regulations) for all studies. Applicable government regulations, University of Arkansas for Medical Sciences research policies and procedures will also be followed. This protocol and any amendments will be submitted and approved by the University of Arkansas for Medical Sciences Institutional Review Board (IRB) to conduct the study. All subjects for this study will be provided a consent form describing this study and providing sufficient information in language suitable for subjects to make an informed decision about their participation in this study. The formal consent of a subject, using the IRB-approved consent form, will be obtained before that subject is submitted to any study procedure. This consent form must be signed by the subject or legally acceptable surrogate, and the investigator-designated research professional obtaining the consent.

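### Exclusion 1 turns on contraindication to beta-blockers rather than on receiving one, so a patient with large, untreated varices can reach the maximal Week -1 CRET with no stated check

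*Combined protocol and SAP*

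**What the plan says.** Exclusion criteria, item 1, joins two conditions: "Large gastric or esophageal varices with contraindication to use beta-blockers". The note below the criteria says that eligibility is taken from the routine transplant work-up. Inclusion criterion 5 accepts active or past variceal bleeding as a qualifying decompensation.

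The Introduction gives the reasoning behind a beta-blocker criterion. In one study the hepatic venous pressure gradient (HVPG) rose by 21% at 50% of maximum work load and was back to normal 5 minutes after stopping. In a second study, "the increase in HVPG during exercise could be abolished if the patient was given a beta-blocker before the exercise bout". The protocol concludes that "data above suggest that the risk of variceal bleeding acutely increases during exercise, whenever the patient is not receiving a beta-blocker".

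Under the CRET heading, every subject has a maximal incremental cycle test at Week -1, Day 1, before randomization, with a "progressively increasing work rate until reaching: volitional exhaustion, or termination by the medical monitor". The Borg scale is used to help titrate the work rate, aiming for 13 to 17. The test is repeated at 12 weeks.

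Risks and Benefits states that CRET staff "are trained to stop the test whenever there are signs for an impending complications", and that the CRET with its ammonia and lactate measurements "would provide the investigator with some sense of risk for complications during intense exercise". It also says: "Although there is a theoretical increased risk for variceal bleeding and HE, these complications have not been observed in prior studies".

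**The concern.** The exclusion and its rationale use different conditions. The rationale concerns what the patient is taking. The exclusion concerns what the patient is able to take. Excluding those who cannot take a beta-blocker protects the rest only if the rest are in fact taking one, and the protocol neither requires nor checks that.

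At stake is the safety of a maximal test given to every participant in both arms. There is also a smaller point of interpretation. The Introduction links a change in VO2max after transplantation partly to stopping a beta-blocker. A change in treatment between the two CRETs could therefore affect a primary fitness measure, and the protocol does not say that it would be recorded.

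**Working it through.** No arithmetic from the plan applies here. The check sets the texts side by side.

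**1. Who passes exclusion 1, among patients with large varices**

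- Contraindication present: excluded.
- No contraindication, on a beta-blocker: eligible, and outside the Introduction's risk condition.
- No contraindication, not on a beta-blocker: eligible, and inside the risk condition.

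No other inclusion or exclusion criterion removes the third group on that ground.

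**2. Is treatment required or checked elsewhere?**

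Beta-blockers are named 4 times in the body text: 3 in the Introduction (once on VO2max after transplantation, twice on HVPG) and 1 in exclusion 1. So 4 − 3 = 1 mention falls in the Approach, and it is the criterion itself. There is none in the activity prescription, Follow Up, the test descriptions, the statistical section or Risks and Benefits. Data collection and handling retrieves items such as endoscopy, pulmonary function and echocardiogram from the medical record, but does not name medication. The Study Calendar has no medication row; its pill count appears to be the check of the amino acid supplement jar described in Follow Up.

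**3. Does another safeguard cover the first CRET?**

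- Stopping at warning signs acts during the test and does not establish treatment status.
- The individual risk information comes from the CRET itself, so it does not exist before the first one.
- Self-chosen intensity applies to the exercise program and the 6-minute walk test (6MWT), and the protocol contrasts the latter with the CRET.
- The clinical check 30 minutes after the test is for hepatic encephalopathy.
- Enquiry about bleeding at each visit detects events after they occur.
- Borg titration to 13–17 is a stated control on effort. It sets no ceiling at or below 50% of maximum work load, and the test is designed to run to exhaustion or termination by the monitor.

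**4. Exposure per affected patient**

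Week -1 plus week 12 gives 1 + 1 = 2 maximal CRETs before any transplant.

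**5. What cannot be computed**

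The documents do not give the number of candidates with large untreated varices, or the combined size and the variceal and beta-blocker status of the earlier study populations. Neither an expected count among the 50 patients nor an upper limit on bleeding risk can be derived.

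**The case against.** The strongest reply is that exclusion 1 rests on standard care. Candidates come from transplant evaluation and hepatology clinics, where a patient with large varices and no contraindication would ordinarily be treated. On that reading the defect is an unstated assumption. This is probably what the authors meant, and it limits how many patients are affected. It does not change what the rule admits as written. The CRET follows a laboratory protocol and a professional statement that are not reproduced, so a pre-test medication review may exist there; the protocol does not say so.

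The evidence of harm is also weak. The Introduction follows its inference about acute risk with a qualification: in the investigators' own randomized trial HVPG fell with exercise (-2.5 versus 4 in controls, p=0.007), and no variceal bleeding was seen in that or other exercise trials in cirrhosis. The fall reflects 12 weeks of training, so it does not answer a concern about a single maximal bout, but it belongs in the account. Across at least 9 studies of activity or exercise testing, some with a bout at 60–100% of VO2max, the protocol reports: "Particularly no episodes of variceal bleeding or HE were observed". It adds that it is unknown whether anyone looked for such events on purpose. These points stand and limit the weight of the concern.

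The remedy is partial too. The Introduction's condition covers any patient without a beta-blocker, not only those with large varices. Its evidence concerns a dose given before exercise, which a current prescription does not show. A strict treatment requirement could also turn away patients whose clinician has chosen other prophylaxis. All three objections are sound, and the fix below allows for the last two.

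**Conclusion.** The mismatch is real. As written, exclusion 1 admits patients with large varices who meet the protocol's own risk condition to a maximal test with no stated check of treatment. It is worth correcting because the correction is cheap, not because harm has been shown.

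A reader might infer that the trial exposes a known group to an established bleeding hazard. The documents do not support that. The risk is inferred from HVPG and not from observed bleeds, it is described as theoretical, the beta-blocker status of patients in the study with the 21% rise is not given, and no count of affected patients is available. A reader might also infer that a chart check would secure all the protection that the Introduction describes. It would not, because untreated patients with smaller varices would still be tested.

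The conclusion assumes that no medication check is contained in the laboratory protocol that is not shown. If one is, the remaining task is to state it in the eligibility criteria.

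**What to change.** Extend exclusion 1 so that, besides contraindication, it covers patients with large varices who are not currently receiving a beta-blocker, unless the investigator documents other variceal prophylaxis and clears the patient for the CRET. Confirm this from the medical record before the Week -1 CRET. An otherwise eligible untreated patient may be deferred until on a stable dose. The documents give no stability period, so the investigators should set one.

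At the Week -1 and week 12 CRETs, record beta-blocker status and whether the usual dose was taken. This matters because the test is done fasting, early in the morning. If treatment has stopped by week 12 in a patient with large varices, the investigator should review the case before the test and document whether it goes ahead. The same records help to interpret VO2max.

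The cost is one reworded criterion, two recorded items at two visits and one review step. Eligibility already comes from routine work-up, so no new test is needed. A few patients will be deferred or not enrolled, and a week 12 CRET may occasionally be postponed or missed; the 6MWT and CT would still be available for the primary aims. A newly started beta-blocker may itself affect VO2max, which is why the dose should be stable before baseline.

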oxygen uptake and carbon dioxide outflow will be performed during the test, in order to determine VO_2 (oxygen consumption) and VCO_2 (carbon dioxide consumption) in real time. The $\text{VO}_{2\text{max}}$ will be identified as a clear plateau in the VO_2 curve. In cases where no plateau can be observed due to exhaustion, the $\text{VO}_{2\text{peak}}$ at the time of test termination will be used as an equivalent. The anaerobic threshold will be identified by means of the V-slope method on the VO_2 to VCO_2 plot (respiratory exchange ratio).(38) Thirty minutes after completion of the test, each patient will be clinically evaluated for clinical signs of HE according to standard criteria (Table 1 and Figure 2). This test will be repeated after completion of the study period (12 weeks), and 6 months after LT.

Ammonia and lactate thresholds (Week -1, Day 1)

In order to obtain frequent venous samples, an 18-20 Ga IV catheter with a saline lock will be placed in the forearm before the test. Ammonia levels will be determined on venous samples with an automated point-of-care device (PocketChem Ammonia Checker II, Arkray Inc., Kyoto, Japan), prior to the start of the test, and then repeated every 3 minutes until termination of test, with a final sample 20 minutes after termination of the test. This will allow identification of the ammonia threshold when results are plotted against % $\text{VO}_{2\text{max}}$. After a baseline determination of lactate, repeated samples will be obtained every 2 minutes, immediately after the test is finished, and 20 min after termination. This will allow correlating the anaerobic threshold obtained from the respiratory exchange ratio with the lactate threshold. For both the ammonia and lactate thresholds is it estimated that 6-7 blood draws will be performed per patient (4 mL per sample) corresponding to 24-28 mL in total. These two tests will be repeated after completion of the study period (12 weeks).

Six-minute walk test (6MWT) (Week -1, Day 3)

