The questionnaire Sickness Impact Profile (SIP) will be used to assess changes in the quality of life. Recent evidence suggests SIP to be superior to SF-36 in detecting health-related quality of life changes occurring in patients with ESLD. Metabolic profile will include determinations of fasting glucose, insulin (in subjects without diabetes mellitus), lipid profile (triglycerides, total-cholesterol, HDL-cholesterol, LDL-cholesterol), and HbA1c. Both SIP and the metabolic profile will be repeated after completion of the study period (12 weeks). The metabolic profile will be repeated 6 months after LT as well.

Randomization

Each participant will be randomly assigned to the active (physical activity + behavioral therapy + nutritional intervention) or control (nutritional intervention) group. The random allocation sequence will be generated using computer-generated random numbers. There will be no stratification in the randomization process, and allocation will be concealed.

Statistical analysis

Subjects sample has been defined by convenience, as there is no precedent for sample estimation. Descriptive statistics will include mean \pm SD and/or median (range), according to distribution of data. Shapiro-Wilk test will be used to assess normal distribution. Results on VCO₂ will be plotted against VO₂, whereas lactate, and ammonia will be plotted against VO_{2max}, for all patients as an aggregate. The lines determining the anaerobic, lactate, and ammonia thresholds will be calculated by linear regression. Continuous variables comparisons within groups will be done with paired t-test or Wilcoxon, whereas between groups will be done with t-test or Mann-Whitney. Categoric variables will be compared with chi-square or Fisher's exact test, as appropriate. Agreement between methods used to address body composition, bioelectrical impedance and DXA, will be investigated with Bland-Altman test.

Data collection and handling

Title: A physical activity program in end-stage liver disease
PI: [name]

Apart from the data generated by the study demographics and clinical information to properly classify the hepatic functional and cardiorespiratory status of each participant will be retrieved from the electronic medical record (EMR). Such information will include results from standard of care laboratories, imaging, and other special studies (EGD, pulmonary function tests, echocardiogram), to calculate MELD score, and Child-Turcotte-Pugh scores.

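### Ammonia has no end-of-test draw, so a patient's ammonia threshold cannot be located in exercise tests under about 9 minutes

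*Combined protocol and SAP*

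**What the plan says.** All references are to the combined protocol and SAP.

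- **Ammonia schedule** (Ammonia and lactate thresholds): one sample before the test, "and then repeated every 3 minutes until termination of test, with a final sample 20 minutes after termination of the test".
- **Lactate schedule** (same section): after a resting sample, "repeated samples will be obtained every 2 minutes, immediately after the test is finished, and 20 min after termination".
- **Number of draws** (same section): for the two thresholds together "is it estimated that 6-7 blood draws will be performed per patient", at 4 mL each, 24-28 mL in total.
- **Definition** (Introduction): the ammonia threshold is "the deflection point at which ammonia production increases disproportionately during CRET". The section on ammonia and lactate thresholds locates it on a plot against percent of VO2max.
- **Analysis** (Statistical analysis): lactate and ammonia are plotted "for all patients as an aggregate". The next sentence reads: "The lines determining the anaerobic, lactate, and ammonia thresholds will be calculated by linear regression". Comparisons of continuous variables "between groups will be done with t-test or Mann-Whitney".
- **Use** (Specific Aims; Physical Activity): change in the ammonia threshold is a secondary aim with an expected advantage for the active arm. Each patient's own thresholds are also meant to inform a safe exercise intensity.

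The duration of the exercise test is not given. It ends at exhaustion or when the monitor stops it.

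**The concern.** A change of slope can be placed only if there are enough points on both sides of it. With samples 3 minutes apart and none at the end of exercise, a short test leaves too few. The 20-minute recovery sample does not help, because it has no position on the exercise axis. The lactate schedule has the end-of-test draw, so the gap is specific to ammonia.

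The ammonia threshold is the only ammonia outcome named in the aims. A patient without a threshold at either visit drops out of that comparison and has no individual threshold to guide exercise. Who drops out depends on how long the patient can pedal, so the loss need not be random. In a short test the ammonia level at the hardest effort can also go unrecorded.

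**Working it through.** **1. The plan's own figure.** 6 x 4 mL = 24 mL and 7 x 4 mL = 28 mL, as stated.

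**2. Test length D (minutes) that fits 6-7 draws.**
- Lactate times alone number 2 + ceil(D/2) (rest, 2-minute grid, end, recovery). This gives 6 for D over 6 to 8 and 7 for D over 8 to 10.
- Distinct times of both schedules together number 6 for D over 4 to 6 and 7 for D over 6 to 8.
- Ammonia times alone number 2 + floor(D/3). This gives 6-7 for D from 12 to under 18, but lactate would then need 8-11 draws, more than the stated total for both.

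The estimate therefore fits tests of roughly 4 to 10 minutes.

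**3. Points needed.** Two lines with an unknown crossing have four parameters: one intercept, two slopes and the crossing point. Take illustrative ammonia values of 50, 55 and 75 at 0, 3 and 6 minutes, with time standing in for percent of VO2max. Crossings at 3, 3.5, 4, 4.5 and 5 minutes all fit with zero residual; only the upper slope changes. Three points do not identify the threshold.

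**4. Ammonia exercise points by schedule.**

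| Test length (min) | As written, 1 + floor(D/3) | 3-minute grid plus end draw | On lactate draws, 1 + ceil(D/2) |
|---|---|---|---|
| over 4 to under 6 | 2 | 3 | 4 |
| 6 | 3 | 3 | 4 |
| over 6 to 8 | 3 | 4 | 5 |
| over 8 to under 9 | 3 | 4 | 6 |
| 9 | 4 | 4 | 6 |
| over 9 to 10 | 4 | 5 | 6 |

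As written, four points require D of at least 9, and from 9 to under 12 minutes the fit has no residual degrees of freedom. In an 8-minute test the last ammonia draw during exercise is at 6 minutes, 75% of the way through.

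**5. Patients with a usable change.** Assumed, not in the documents: D normal with mean 8, 9 or 10 and SD 2; correlation 0.7 between the two tests; training adds 1-2 minutes; a value exists if D is at least 9. By simulation with at least a million patients per arm:

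| Mean D | Control, both tests usable | Active, both tests usable |
|---|---|---|
| 8 | 0.198 x 25 = 5 | 0.259-0.293 x 25 = 6-7 |
| 9 | 0.373 x 25 = 9 | 0.451-0.486 x 25 = 11-12 |
| 10 | 0.581 x 25 = 15 | 0.654-0.682 x 25 = 16-17 |

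**6. Possible bias in the arm difference in change.** Further assumptions: threshold SD 8 points of percent VO2max, correlation 0.3-0.5 with the length of the same test, true gain 5 points. Among patients with both tests usable, the difference in change is 3.9-4.6 (mean 8), 4.2-4.7 (mean 9) and 4.5-4.8 (mean 10). Against 5, the shortfall runs from 1 - 4.8/5 = 4% to 1 - 3.9/5 = 22%. In the control arm, selection is the same at both visits and cancels. In the active arm the 9-minute limit is easier to reach at week 12, so baseline values are selected upward more than week-12 values and the change is understated.

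**The case against.** **The fit may be pooled.** The Statistical analysis section can be read as one fit over all patients, to which short tests still contribute points. That is a fair reading, and no per-patient algorithm is written. But a pooled fit gives one crossing per group and visit. It supplies no patient values for the t-test or Mann-Whitney, nor for the individual use in the Physical Activity section.

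**The wording may include an end sample.** Sampling until termination could be taken to include a draw at that moment. The limit then falls to 6 minutes or less. The separate end-of-test draw for lactate makes this the less natural reading, but it cannot be excluded.

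**Test length is inferred.** It comes from a rough logistics figure, and the laboratory's exercise protocol is not in the documents. A reader might infer that the tests are known to be too short. They are not: the draw estimate may simply be too low, and tests of 12 to under 18 minutes would give 5-6 ammonia points. This stands, and it limits how firmly the loss can be stated.

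**The bias could be read as larger.** Comparing week-12 thresholds between arms among patients with a week-12 value gives 2.5-4.5 against a true 5 under the same assumptions, or 11% to 51% too small. The aim is change from baseline, so that is the wrong comparison. Nor do the documents say that training lengthens the test. The Introduction says that "a more efficient aerobic capacity is associated with higher ammonia thresholds", which concerns aerobic capacity, not minutes on the ergometer, and work rate is titrated with a perceived-exertion scale.

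**Safety data are not absent.** Raw ammonia values, a 20-minute sample and a clinical encephalopathy check at 30 minutes are all collected, and Risks and Benefits relies on the determinations as well as the thresholds. What is missing is ammonia at peak effort.

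**Conclusion.** The point holds as a sampling and specification gap in one secondary outcome. As written, a patient's ammonia threshold is not identifiable in a test under 9 minutes, or of 6 minutes or less on the lenient reading. This rests on a two-line fit per patient, the natural reading of a deflection point found from regression lines and the only one that serves the planned between-group tests.

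The main consequence is lost data: 5-15 of 25 control and 6-17 of 25 active patients with a usable change, on assumed test lengths. A bias toward no difference of about 4% to 22% is possible, but only if training lengthens the test and the threshold correlates with test length. Both are assumptions, so the bias is a secondary reason to act. The documents support neither a firm claim that tests will be too short nor a claim that exercise safety goes unmonitored. The change is still worth making, because time points not sampled cannot be recovered later.

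**What to change.** **Ammonia and lactate thresholds section.** Measure ammonia on the draws already taken for lactate: rest, every 2 minutes, end of test and 20 minutes after. This gives at least four exercise points for any test over 4 minutes. If the analyser cannot keep that pace, keep the 3-minute grid and add ammonia to the existing end-of-test lactate draw, which gives four points for any test over 6 minutes.

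**Statistical analysis section.** Fit the two lines per patient and per test, and keep the pooled plot as illustration. Report by arm and visit how many thresholds could not be located.

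**Cost.** There is no extra venepuncture. With the first option, distinct draw times fall from 7 to 6 for tests over 6 to 8 minutes and from 8-9 to 7 for tests over 8 to 10 minutes, which matches the 6-7 estimate. More ammonia assays are run per test, and samples may have to wait for the analyser. Individual fits on 4-6 points stay noisy. For tests of 7-10 minutes, with assumed noise of 5% or 10% of the peak rise, the error is about 6-10 or 13-19 points of percent VO2max. That is no more precise than a 3-minute fit where one exists; the gain is that nearly every patient has a value. With only four points, as in tests over 4 to 6 minutes, there are still no residual degrees of freedom. No additional encephalopathy grading is needed.
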